13.2.1 Stratification and Randomization

All participants must have at least two semen samples before enrollment, at least one of which has detectable Ebola virus RNA, in order to be eligible for this study. Subjects will be stratified based on whether screening samples both had detectable Ebola virus RNA, or only one of the two had detectable Ebola virus RNA. Recruitment will focus on PREVAIL III participants with evidence of repeated samples with detectable Ebola virus RNA or CT values <39 on a single sample to try to enroll people likely to have detectable RNA on two screening samples, but participants may be enrolled from outside of PREVAIL III as well. Subjects will also be stratified based on the country in which they reside. There are substantial differences between countries in how the epidemic unfolded and how those with EVD were treated.

Subjects will be randomized 1:1 within the strata defined above.

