13.3.1 Power Calculations

The table below lists the simulated power to find a significant difference in treatment-phase ANR and follow-up ANR for various true rates of ANR in the placebo and GS-5734 arms. With 50 people (25/arm), we will have reasonable power (>80%) to find a difference in both the treatment-phase ANR and the follow-up ANR if the effect of treatment is to cut the probability of a detectable sample by 50% for each person at each time, starting at day 3. If the effect of treatment is instead that 40% of people experience sterilization starting on day 3, such that their probability of a detectable sample drops to 0 (except for false positives), and the rest of the people are unaffected, then the power varies depending on the amount of heterogeneity in the probabilities.

ANR p-value based on t-test on proportion negative at 6 (day 3 to day 28) or 5 (week 8 to week 24) visits. All power estimates based on 1,000 simulations, 1% false positive rate, and 5% false negative rate, alpha=.05, no adjustments for multiple comparisons.

Ν	P _i =P(detectable person i) Control group	Treatment Effect	Power d3- d28 ANR	Power w8- w24 ANR
50	pi=.5	.5	.96	.98
	p _i ~Beta(10,10)	(multiplicative on probability)	.93	.97
	$p_i \sim U(0,1)$	starting d5	.95	.98
	$p_i = \begin{cases} . \ 1 \ with \ 50\% \ chance \\ . \ 9 \ with \ 50\% \ chance \end{cases}$.97	.99
50	p _i =.5	.4	.77	.84
	pi~Beta(10,10)	(Probability sterilize)	.85	.89
	$p_i {\sim} U(0,\!1)$	starting d5	.16	.23

Table 11	. Power	for	endpoints	under	varying	assumptions.
----------	---------	-----	-----------	-------	---------	--------------

		Р	REVAIL IV
		,	Version 10.0
		1	3 May 2019
$p_i = \begin{cases} . \ 1 \ with \ 50\% \ chance \\ . \ 9 \ with \ 50\% \ chance \end{cases}$.52	.67	

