13.4 Statistical Analyses

The primary analysis of treatment-period ANR will be conducted once subjects have completed their 28-day follow up and reviewed by the DSMB. The follow-up ANR can be conducted once all subjects have completed the week 24 visit. ANR will be computed as the proportion of assays in a specified window that are negative. For the primary analysis, any returned CT value will be considered a positive PCR.

The primary analysis will be based on an Intention-to-Treat framework, in which participants are analyzed in the group to which they are randomized, including participants who reduce or discontinue their individual dosing. In the event that the DSMB recommends a study-wide dose reduction, the primary analysis will remain all people randomized to treatment, regardless of dose, compared to all people randomized to control, but the DSMB can recommend increasing the sample size at that point so there are sufficient people at the lower dose for secondary analyses.

The primary analyses of ANR during the treatment phase and during the follow-up phase will be based on a two-sided permutation test comparing the groups (i.e. using a 2 sample t-test to define the test but use its permutation distribution to compute significance). This will be stratified by number of detectable samples during screening and country, as was done for randomization. No multiplicity adjustment will be imposed on the primary analyses of the ANR from the two different time periods.

As the expectation is that the study will be fully enrolled before we have sufficient data collected on the follow-up phase, there are no formal stopping rules for efficacy or futility.

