Appendix B: Schedule of Procedures/Evaluations

PREVAIL IV Version 10.0 13 May 2019

Assessment for Adverse events				Х	Х	Х	Х	Х	Х	Х	Х	Х	Х	Х	Х	Х	Х	Х
Review of concomitant meds		Х	Х		Х	Х	Х	Х	Х	Х	Х	Х	Х	Х	Х	Х	Х	Х
Participant satisfaction survey													Х					Х
Blood Samples																		
Chemistries, total and direct bilirubin, AST/ALT, and lipids		Х	Х		Xj	Xj	Xj	Xj	Х	Х	Х	Х	Х	Х	Х	Х	Х	Х
CBC with diff		Х	Х		Xj	Xj	Xj	Xj	Х	Х	Х	Х	Х	Х	Х	Х	Х	Х
Prothrombin time (PT), aPTT, INR, and D-dimer		Х	Х		Xj	Xj	Xj	Xj	Х	Х	Х	X	Х	Х	Х	Х	Х	Х
Leftover serum and plasma storage		Х	X ⁿ		Xj	Xj	Xj	Xj	Х	Х	Х	Х	Х	Х	Х	Х	Х	Х
GS-5734 PK and metabolites - plasma ^o				\mathbf{X}^{h}			Xj	X ^h										
PBMCs for intracellular concentrations - PK°								Xi										
eGFR		Х																
Ebola antibody levels		Х																Х
Semen Samples Ebola PCR with CT for NP & GP	Xb	X ^m					X ^k		Х	Х	Х	Х	Х	Х	Х	Х	Х	Х
Ophthalmologic Exam	Xe																	X^1
HIV and Syphilis Test		X ^p																

^a Participants in Guinea can sign a pre-screening informed consent form for semen collection and testing. Procedures conducted under PREVAIL III will be accepted for PREVAIL IV pre-screening.

^b Positive PCR for NP or GP using the GeneXpert assay at pre-screening in at least one of two or more semen samples within 42 days of randomization.

^c On infusion days, vital signs will be obtained within 30 minutes prior to start of infusion and 30 minutes and 60 minutes after infusion completes.

^d Performed only if needed to evaluate new symptoms/complaints.

^e Baseline ophthalmologic exam to be conducted within 4 months of enrollment in PREVAIL IV. The baseline ophthalmologic exam can be extracted from PREVAIL III data if done within 4 months prior to enrollment in PREVAIL IV. Ophthalmologic exams must be repeated if conducted > 4 months prior to enrollment in PREVAIL IV or if they were not previously done.

^f Beginning & end of Treatment phase with DSMB evaluation planned for end of treatment phase.

^g Beginning & end of Follow up phase.

^h Draw immediately after infusion if possible and not later than 5 minutes after infusion.

ⁱ Draw within 1 hour after infusion, but may be drawn with the PK plasma sample drawn within 5 minutes after infusion.

^j Pre-infusion sample.

^k Day 4 semen samples can +1 e.g. on days 4 or 5 but only one semen sample is needed during infusion.

¹End of study ophthalmologic exam to be done at 24 weeks +/- 6 weeks

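### Both primary ANR analyses leave out the quantitative screening CT value; pre-specifying it as a covariate is valid and cheap, but the size of the gain is not settled by the documents

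*Combined protocol and SAP*

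**What the plan says.** Section 13.4 bases both primary ANR comparisons on a "two-sided permutation test comparing the groups", with the two-sample t as the statistic. On baseline information it says only: "This will be stratified by number of detectable samples during screening and country, as was done for randomization". If missingness is substantial, a weighted linear regression with an arm indicator replaces the t-test; no other covariate is named.

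Section 13.2.1 defines the strata as one versus two detectable screening samples, and country: "Subjects will be randomized 1:1 within the strata defined above".

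Screening CT is collected: the semen row of Appendix B reads "Ebola PCR with CT for NP & GP". At least one of two screening samples must be positive, so every eligible man has at least one CT value. The plan uses that value in three places:
- Recruitment (13.2.1) favours men with repeated detection or "CT values <39 on a single sample to try to enroll people likely to have detectable RNA"; the sentence goes on to specify two screening samples.
- The enrolment target (13.3) accepts 30 men with CT below 39 as an alternative to 20 men with two detectable samples.
- A secondary objective (2.2.1) singles out men with CT of 39 or lower.

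CT trajectories appear in the analysis only as a secondary censored regression (13.4.1).

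**The concern.** The endpoint is a proportion over five or six visits per man, with about 30 men per arm. If men differ in their underlying tendency to shed, that difference adds to the variance of the arm comparison. A one-versus-two count captures part of it; CT is a continuous measurement on the same samples and may capture more. Section 13.3 says that enrolment is limited by the number of men with detectable virus, so any variance removed by baseline data already in hand stands in for men who may not be recruitable. Adjustment would also correct chance imbalance in baseline viral level within strata.

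**Working it through.** **1. The plan's own power figures.** Inputs from 13.3.1: 25 per arm; "All power estimates based on 1,000 simulations, 1% false positive rate, and 5% false negative rate, alpha=.05, no adjustments for multiple comparisons"; "ANR p-value based on t-test on proportion negative at 6 (day 3 to day 28) or 5 (week 8 to week 24) visits". Observed detection probability = 0.95p + 0.01(1-p). I drew p conditional on at least one of two positive screening samples and used a linear-model t-test on arm and the one-versus-two stratum, as an approximation to the stratified permutation test. Country was not simulated.

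- Halving, follow-up: .970/.963/.973/.995 against .98/.97/.98/.99 in Table 11. Reproduced within 2 points.
- Halving, treatment phase, day 4 unaffected (Table 11 starts the effect at d5, the text at day 3): .932/.915/.925/.974 against .96/.93/.95/.97. Two of four rows are within 2 points.
- 40% sterilised: not reproduced by any one variant. U(0,1) gives .57-.75 against .16/.23.

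Gains are therefore measured against recomputed baselines, not against Table 11.

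**2. Adding CT under Table 11's distributions** (25 per arm; squared correlation of CT with p assumed to be .10 / .25 / .50):

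| Scenario | Strata only | Strata + CT |
|---|---|---|
| Sterilised, 6 visits, p=.5 | .746 | .738/.739/.738 |
| Sterilised, 6 visits, Beta(10,10) | .722 | .708/.721/.727 |
| Sterilised, 6 visits, U(0,1) | .707 | .707/.728/.751 |
| Sterilised, 6 visits, .1/.9 mixture | .795 | .793/.811/.841 |
| Sterilised, day 4 unaffected, U(0,1) | .609 | .610/.630/.668 |
| Halving, day 4 unaffected, U(0,1) | .925 | .930/.938/.960 |

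Across all scenarios the change runs from about -1 to +6 points. Type I error with CT was .049 to .055.

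**3. Adding CT under a beta fit to the counts in 13.3.** Of 134 men, 100 were never detectable, 21 once and 13 twice.

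- E[p] = (21/2 + 13)/134 = .175; E[p²] = 13/134 = .097.
- Intraclass correlation = (.097 - .175²)/(.175 × .825) = .46, giving Beta(.207, .975).
- Given one positive: Beta(1.207, 1.975), mean .379, variance .0563. Given two: Beta(2.207, .975), mean .694, variance .0508.
- Within-stratum between-man variance = (21/34)(.0563) + (13/34)(.0508) = .054.
- Adding the between-stratum part, (21/34)(13/34)(.694 - .379)² = .023, gives a total of .078.
- Visit-level variance = E[p(1-p)]/6 = .0287.
- Residual after strata = .054 + .0287 = .083, of which .054/.083, about 65%, is between men.

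If CT explains 25% of the .054, the residual is .069 (down 16%); at 50% it is .056 (down 33%). These are worth about 20% and 50% more men (.083/.069 and .083/.056).

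Simulated power at N=60, assay errors as above, day 4 unaffected in the treatment phase:

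| Scenario | Strata only | CT explains 25% / 50% |
|---|---|---|
| Halving, treatment phase | .84 | .88 / .93 |
| Sterilised, treatment phase | .53 | .56 / .61 |
| Halving, follow-up | .93 | .95 / .97 |
| Sterilised, follow-up | .62 | .65 / .69 |

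Repeat runs put the treatment-phase gain at about 3 to 8 points; rounding in the table stretches one cell to 9. At 10% explained the gain was about 0 to 1 point. Type I error was .052.

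**4. A second model that fits the same counts.** Let a share of men shed with one common p and the rest never. Then p = .097/.175 = .553 and the share is .175/.553 = .317. This returns 100/21/13 exactly. Every eligible man then has the same p, so nothing is left for CT to explain. Power at N=60 goes from .986 to .984 (halving) and from .768 to .762 (sterilised); with two uninformative covariates, from .985 to .982 and from .764 to .751.

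**The case against.** The strongest reply is that the planned test is valid, matches the randomisation and already carries baseline viral status. Section 13.2.1 uses CT to predict two positive screening samples, which is the stratification factor itself, so CT may add little. Section 1.1 calls shedding intermittent and quantitatively variable. This stands as a limit on the gain. It does not show that a continuous measurement is exhausted by a yes/no count, and ANR averages over visits.

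Second, two samples per man identify only E[p] and E[p²]. The within-stratum variance of .054 comes from the beta shape, and step 4 shows an equally good fit where it is zero. Section 13.3 itself says that the type of heterogeneity is unclear. This stands in full.

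Third, a change now comes mid-trial. Section 1.1 reports 34 men enrolled, and under 11.7.1.1 the study statistician prepares by-arm reports and attends closed sessions. This stands, and it governs who may write the amendment and when.

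A reader might also want time since EVD onset in the model, citing the fall from 65% to 26% detection in Section 1.1. Those survivors were not selected for a recent positive sample, as men in this trial are, so the figure does not carry over directly.

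**Conclusion.** The omission is real: screening CT enters neither the primary permutation test nor its weighted replacement, although every eligible man has a value and the plan relies on it elsewhere. It is a missed opportunity for precision, not an error or a bias.

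A reader might infer that the plan gives up free precision on both primary endpoints and that PREVAIL III shows how much. The documents do not support this. The explained share of 25-50% is an assumption without a source, and the variance it acts on depends on a chosen distribution. The plausible range at N=60 is about -1 to +8 points in the treatment phase. For follow-up the simulated gain of 2 to 7 points also assumes that screening CT still predicts shedding at weeks 8-24, which no document figure shows. The case for the change is that the possible loss is about one point, the possible gain is several, and type I error is preserved.

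**What to change.** In 13.4, define the statistic for each primary ANR comparison as the t-value of the arm coefficient from a linear regression of per-man ANR on arm, randomisation strata and one screening CT covariate. Take significance by permuting arm within randomisation strata. Put the same covariate in the weighted regression for missing data. Keep the unadjusted stratified test as a sensitivity analysis.

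Define the covariate once, for example as the lowest NP or GP CT over the two qualifying screening samples in the 42-day window. Say which two count, because some men give more than two and a minimum depends on how many are taken. If a cut-off is used instead, reconcile below 39 (13.2.1, 13.3) with 39 or lower (2.2.1). Time since EVD onset is optional.

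The explained share could be estimated from PREVAIL III longitudinal data before the change is made. The amendment should be written before any unblinded efficacy analysis, by staff who have not seen by-arm data, and say so.

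Cost: one or two degrees of freedom, SAP wording, a little code and a dated amendment. No new data are needed.

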13.4.1 Secondary Endpoints

Secondary analyses or safety and tolerability endpoints will include tabulation of grade 2 and higher laboratory values, including but not limited to ALT and AST, and adverse events by treatment arm.

Secondary analyses will examine the effect of defining a positive CT value to be any reading of 40 or lower, as well as the main analysis based on a per-protocol definition of treatment arm. Other secondary analyses will include per protocol analyses, Generalized Estimating Equations models for the serial binary endpoints of detectability, exact tests of proportions for binary endpoints such as Sustained Negativity Rate (no detectable Ebola RNA at any included time point), and censored regression models to compare CT trajectories will also be performed.

In the event that the study-wide dose is reduced to 75 mg, a secondary analysis will be restricted to people on both arms enrolled after the dose reduction.

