To assess and characterize the persistence of Ebola viral RNA in semen, men enrolled in PREVAIL III are invited at their 6-month visit and beyond to undergo counseling and donate semen for testing of the presence of Ebola virus RNA. Semen testing is conducted at the Liberian Institute of Biomedical Research (LIBR) and the Guinean Viral Hemorrhagic Fever labs using the glycoprotein (GP) and nucleoprotein (NP) target genes on the Cepheid GeneXpert platform. The GeneXpert platform has shown superior sensitivity for detection of Ebola viral RNA, particularly in semen, at low levels of Ebola viral RNA, over other Taqman based assays in both published and unpublished studies.¹²⁻¹⁴

In the Liberian PREVAIL III study men with initial Ebola virus RNA detection are asked to continue to donate every two weeks, whereas men with an initial lack of detection, or a negative test, return to donate semen for testing every 4-6 weeks. Each time a subject donates semen, he returns for the test result and counseling on condom use within two weeks. At that time, he is advised on the frequency of follow-up. Upon repeat testing, approximately 30.7% of the 279 seropositive male survivors in PREVAIL III have had at least one semen sample with detection of Ebola virus RNA. Figure 1 summarizes the CT values for the 83 men who have had at least one semen sample with detection of Ebola virus, sorted by date of most recent specimen collection. Each individual participant is a row, with samples from the same individual connected by horizontal lines. White dots indicate samples where Ebola virus RNA was not detected; black dots indicate samples for which Ebola virus RNA was detected with a CT between 40 and 45; red dots indicate an observed CT value below 40. The displayed CT value is based on the minimum CT of NP or GP from the same sample. Of note, once a male has enrolled

in PREVAIL IV his data is no longer included in this plot, so it is slightly biased towards less positivity. As of August 2017, 257 male survivors enrolled in PREVAIL III had donated at least two semen samples for Ebola virus RNA testing. Seminal Ebola virus RNA shedding appears to be intermittent over time and quantitatively variable. The longest reported duration for detection of Ebola viral RNA in semen was 40 months following EVD.¹⁵

Figure 1. Minimum CT(NP,GP) results among those with at least 1 detectable sample from PREVAIL III (n=83)

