4.3 Subject Inclusion Criteria

Individuals must meet all of the following criteria to be eligible for study participation:

- Men ≥ 18 years of age.
- One of two semen samples with Ebola virus RNA detection (defined as a positive PCR for NP or GP using the GeneXpert assay within 42 days prior to randomization).
- Willingness to be available for study evaluations for 6 months.
- Willingness to allow storage of biological samples.
- Willingness to be followed by a Participant Tracker.
- Willingness to refrain from alcohol consumption for study days -7 to 14.
- Willingness to comply with MOH & CDC guidance on using a condom for sexual activity and at least through week 24 of the study.

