13.3 Sample Size Justification

Preliminary data from PREVAIL III was used to estimate the rates of detectable virus in semen of survivors. Among 134 men who contributed at least two semen samples, we analyzed the last two semen samples per person. One hundred men had undetectable CT at both time points, 13 (10%) were detectable at both time points, and 21 (16%) had mixed detectability (detectable/undetectable or undetectable/detectable). Based on these estimates, 26% of male survivors may be eligible for the study.

We use this data to estimate the proportion of men who might be eligible for the study as well as the "success" rate among placebos. The enrollment is limited by the number of available subjects with detectable Ebola virus in semen at screening. Based on semen testing in PREVAIL III, approximately 26% of male survivors will have detectable seminal Ebola viral RNA when tested longitudinally during the first 1-2 year window. This percentage may decrease with time.

Based on the power calculations below, complete data on 50 men (25/arm) should be adequate to find a difference under many assumptions. However, as the power calculations do not take into account missing data, nor is it clear what type of heterogeneity or treatment effect might be more realistic, the study will attempt to enroll at least 60 people (30/group), with a target of at least 20 participants with two screening samples with a detectable CT or at least 30 participants have an Ebola NP or GP CT value using the Cepheid of <39. If the total sample size of 60 is enrolled without 20 people with two detectable samples, or at least 30 participants with an Ebola NP or GP CT value using the Cepheid of <39 we will continue to enroll until one of these criteria is met up to a total of 120 people if possible.

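### The CT ≤40 secondary analysis takes no account of screening CT, although men may enter on detections above 40, so it loses precision and is hard to read as a threshold check

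*Combined protocol and SAP*

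**What the plan says.** - **Entry (4.3).** The criterion is "One of two semen samples with Ebola virus RNA detection (defined as a positive PCR for NP or GP using the GeneXpert assay". The sample must fall in the 42-day window before randomisation. The criterion sets no upper limit on CT.
- **Readings above 40 occur (1.1).** In the description of Figure 1, "black dots indicate samples for which Ebola virus RNA was detected with a CT between 40 and 45". The same section states: "Seminal Ebola virus RNA shedding appears to be intermittent over time and quantitatively variable".
- **Primary definition (13.4).** "For the primary analysis, any returned CT value will be considered a positive PCR". Every entrant's qualifying sample is therefore positive on the primary scale.
- **Secondary definition (13.4.1).** "Secondary analyses will examine the effect of defining a positive CT value to be any reading of 40 or lower". No restriction to men who had such a reading at screening is written, and no adjustment for screening CT.
- **Strata (13.2.1, 13.4).** Randomisation and the permutation test are stratified by number of detectable screening samples and by country. CT is not a factor.
- **Enrichment (13.3).** Enrolment aims for "at least 20 participants with two screening samples with a detectable CT or at least 30 participants have an Ebola NP or GP CT" below 39. Either condition is enough.
- **Related analyses.** Section 2.2.1 has a secondary objective comparing the arms in men with a pre-entry CT of 39 or lower. Section 13.4.1 also plans censored regression of CT trajectories.

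**The concern.** Entry and the secondary outcome use different definitions of positive. A man whose screening detections all lay between 40 and 45 enters as positive, but on the CT ≤40 scale he is negative before his first dose. If his later samples behave the same way, he contributes high negativity in either arm.

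This has two consequences. The absolute difference in ANR is averaged over men with little room to change. The mixture of men near and well below the cut also adds between-man variance that the arm comparison must absorb.

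The analysis is there to show whether the result depends on the positivity threshold. As written, a smaller or non-significant difference at CT ≤40 could reflect who was enrolled rather than what the drug did at higher viral load, and the reader could not tell which.

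**Working it through.** **1. Reproduce the plan's figure.** Table 11, first row: 25 men per arm, control probability of detection 0.5, effect a 50% cut, 1% false positives, 5% false negatives, two-sided alpha 0.05.

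- P(positive) = 0.95p + 0.01(1 − p).
- Control: 0.475 + 0.005 = 0.480. Treated (p = 0.25): 0.2375 + 0.0075 = 0.245. Difference 0.235.
- Simulated power for weeks 8–24 (5 visits) is 0.97, against 0.98 stated. For the treatment phase (6 visits, first unaffected) it is about 0.94, against 0.96 stated.

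These figures are for the any-CT definition. The plan states no power for the CT ≤40 analysis.

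**2. Worst case for the CT ≤40 cut.** Let a share f of men in both arms never read 40 or lower. The difference becomes (1 − f) × 0.235. With 30 per arm, weeks 8–24, unstratified t-test:

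| f | Difference, all men | Power, all men | Power, remaining men only |
|---|---|---|---|
| 0 | 0.235 | 0.99 | 0.99 |
| 0.25 | 0.18 | 0.79 | 0.95 |
| 0.50 | 0.12 | 0.46 | 0.84 |

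Type I error stays at 0.05 for each f.

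**3. What bounds f?** If enrolment stops at 60 on the CT <39 condition, f is at most 30/60 = 0.50. If it stops at 120 with 30 such men, f is at most 90/120 = 0.75. If it stops on the two-detections condition, the documents set no bound. These are ceilings, not estimates: a man outside the CT <39 count may still lie between 39 and 40, and the target is a minimum.

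**4. A more realistic model, with the planned detection stratum.** All CT parameters here are assumptions. Man-mean CT is normal (mean 38 to 43, SD 3 to 4), with sample-to-sample SD 2 to 3. Detection is CT ≤45 and entry needs at least one of two detections. There are 30 men per arm, randomised within one-versus-two detections, and six samples each. The drug removes each CT ≤40 reading with probability 0.5. Country is left out. A linear model on each man's proportion negative stands in for the permutation test. There were 2,000 trials per setting, so Monte Carlo error is about 1 point. Ranges show repeat runs.

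| Mean / SD / noise | No screening CT ≤40 | Power, planned stratum | Plus screening flag | Restricted to flag |
|---|---|---|---|---|
| 38 / 4 / 2 | 21% | 0.99 | 1.00 | 1.00 |
| 41 / 3 / 3 | 39% | 0.90–0.91 | 0.93 | 0.86–0.87 |
| 42 / 4 / 2 | 49% | 0.73–0.74 | 0.87–0.88 | 0.82–0.84 |
| 42 / 3 / 3 | 47% | 0.79–0.82 | 0.84 | 0.71–0.72 |
| 43 / 3 / 3 | 56% | 0.67–0.71 | 0.72 | 0.53–0.55 |

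- Over the whole grid, 16% (38/3/3) to 64% (43/3/2) of entrants have no screening CT ≤40.
- At mean 40 to 43, untreated men without the flag are negative at CT ≤40 in about 73% to 90% of samples.
- Within the same run, adding the flag raised power by about 1 to 15 points in all 16 settings at mean 40 to 43.
- In the 42/4/2 example the difference is about 0.20 in all men and 0.33 in flagged men. Adjustment leaves the all-men difference at about 0.20: it restores precision, not the size of the difference.

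**5. Chance imbalance.** If 30 of 60 men entered above 40 and CT played no part in allocation, the arms would differ by 6 or more such men with probability about 0.20.

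**The case against.** The strongest reply is that nothing here is invalid. Changing the threshold while keeping all randomised men fits the intention-to-treat framework in 13.4, and a smaller difference in that population is a correct estimate for it. No decision rule rests on this analysis. That stands, and it limits the point to precision and interpretation.

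A reader might go further and infer that untreated men counted as responders fill both arms, or that men entering above 40 cannot show an effect. The documents do not support either. ANR is each man's proportion of negative samples, not a responder count. Sustained negativity is defined by no detectable RNA, not by CT ≤40. Shedding is described as intermittent and variable, so a man above 40 at screening can later read lower; in the simulation he does so in about 10% to 27% of samples. The share of such men is not given, and recruitment under 13.2.1 favours repeated detection or low CT.

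The planned stratification also absorbs part of the variance, because number of detections tracks CT. In the 42/4/2 example an unstratified test gives 0.65 to 0.67, and the planned stratum alone raises it to about 0.73.

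Restriction is not a safe remedy. It loses power when CT is noisy. If the drug instead raised CT by 2 cycles (an assumption), the example gives 0.44 restricted against 0.49 in all men with the planned stratum.

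Finally, the CT ≤39 subgroup objective and the censored CT regression address part of the same question. But 13.4.1 does not link that subgroup to the CT ≤40 outcome, and neither analysis improves the CT ≤40 comparison itself.

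**Conclusion.** The point holds as one about precision and interpretation in a secondary analysis. Men may enter with every screening reading above the cut used to define the outcome, and neither the strata nor the analysis text takes account of it. The absolute ANR difference shrinks and avoidable variance remains. Type I error is not raised, and the primary any-CT comparison is untouched.

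The size depends on a CT distribution that the documents do not give. Under the assumed range, the affected share is about 16% to 64%, and adjusting for the screening flag is worth about 1 to 15 points of power at mean CT 40 to 43. At mean 38 power is already about 0.99 or higher and the change makes no practical difference. The case for acting rests on low cost and a clearer threshold check, not on a demonstrated failure of the analysis.

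**What to change.** In 13.4.1, state that the CT ≤40 analysis:

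1. keeps all randomised men and the planned strata;
2. also adjusts for, or stratifies by, whether any semen sample in the 42-day window before randomisation had NP or GP CT ≤40;
3. tabulates the number of men in each flag group by arm.

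A workable form is to permute within the planned strata and take as test statistic the arm coefficient from a linear regression that includes the flag. Section 13.4 already allows a regression coefficient when many samples are missing. This avoids sparse cells from crossing three binary factors (2 × 2 × 2 = 8 cells in as few as 60 men).

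The same comparison in flagged men only can be listed as supportive. It describes men who entered with CT ≤40, but it has fewer men and can have less power.

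The cost is a sentence or two of wording. Appendix B already schedules CT for NP and GP on the pre-screening and screening samples, so no new data are needed. The flag is fixed before randomisation, so the randomised comparison is preserved.

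### Section 13.4.1 does not carry the randomisation strata into the SNR exact test, GEE or censored regression; run unstratified, the SNR test and GEE are conservative and lose some power

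*Combined protocol and SAP*

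**What the plan says.** Section 13.2.1 defines strata by country and by whether one or both screening samples were detectable, and states: "Subjects will be randomized 1:1 within the strata defined above". Section 13.4 bases the primary ANR comparisons on a "two-sided permutation test comparing the groups" and adds: "This will be stratified by number of detectable samples during screening and country, as was done for randomization".

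Section 13.4.1 names "Generalized Estimating Equations models for the serial binary endpoints of detectability, exact tests of proportions for binary endpoints such as Sustained Negativity Rate" (defined there as no positive result at any of the visits counted), together with censored regression for CT trajectories. For none of these does it mention strata, covariates, a working correlation or a variance estimator. It neither includes nor excludes the strata.

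SNR is a listed follow-up objective (2.2.2) and endpoint (3.2.2.2). The only significance level and power figures are in 13.3.1 and concern ANR ("alpha=.05, no adjustments for multiple comparisons"). None is given for the secondary analyses.

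**The concern.** Stratified randomisation balances the arms on the stratum factors, so the treatment comparison varies less from trial to trial than an unstratified analysis assumes. If a factor is prognostic and the analysis leaves it out, the standard error is too wide, true size falls below nominal and power is lost. The number of detectable screening samples should predict later detection, so it is a factor of this kind.

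Two things are at stake. An SNR comparison with about 60 men has little power to spare if treatment only halves detection. And if covariates and the variance estimator stay open, the analyst can choose after the fact between GEE versions whose true size runs from about 3% to about 6%.

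**Working it through.** **The plan's own figure.** Table 11 covers only the ANR t-test at N=50. For p=.5 with detection halved it gives .96 (days 3 to 28) and .98 (weeks 8 to 24). Re-simulation gives 0.94 (one visit before the effect starts) to 0.99 (all six visits affected), and 0.97. Other rows reproduce in part, and no sterilisation cell does. None of this bears on the secondary tests.

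**How prognostic is the stratum?** Of 134 men in 13.3, 13 were detectable twice, 21 once and 100 never. A beta distribution for each man's detection probability, fitted by moments:
- m = (21/2 + 13)/134 = 0.175; E[p²] = 13/134 = 0.097
- ρ = (0.097 − 0.175²)/(0.175 × 0.825) = 0.458; a + b = 1/ρ − 1 = 1.183; so a = 0.207, b = 0.975
- One positive, Beta(a+1, b+1): mean 1.207/3.183 = 0.38
- Two positive, Beta(a+2, b): mean 2.207/3.183 = 0.69
- Five-visit placebo SNR for Beta(A, B) = ∏(B+k)/(A+B+k), k = 0 to 4: 0.227 (one positive) and 0.037 (two positive)

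The two-positive share is 13/34 = 38%, or 23 of 60 men, leaving 37. Expected sustained negatives under no effect: 37 × 0.227 + 23 × 0.037 ≈ 9 of 60.

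**SNR exact test, N=60.** Two-sided p by point probability, using one hypergeometric (plain) or convolved stratum hypergeometrics (stratified). Under 40% cleared, treated SNR is 0.4 + 0.6 × 0.227 = 0.536 and 0.4 + 0.6 × 0.037 = 0.422. Under halving it is E[(1 − p/2)⁵] = 0.422 and 0.160. Strata of 37 and 23 are odd, so an even split leaves one spare man in each, and it matters which arm gets him. The first two rows are full enumeration (two strata). The third is 6,000 simulated trials with four strata and permuted blocks of 4; the plan states no block scheme.

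| Allocation (active/placebo) | Size, plain → stratified | Power, detection halved | Power, 40% cleared |
|---|---|---|---|
| 19/18 and 11/12 | 1.4% → 3.2% | 24.8% → 26.8% | 76.4% → 78.1% |
| 18/19 and 12/11 | 1.4% → 3.2% | 20.5% → 30.9% | 73.2% → 80.4% |
| Blocks of 4 | 2.2% → 2.9% | 25.1% → 28.9% | 76.3% → 79.2% |

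The gain from stratifying alone is therefore about 2 to 10 points. Stratified mid-p has size 4.2 to 4.7%. In the first allocation its power is about 31% and 81%.

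**Discreteness or strata?** Under blocks of 4, the plain test has size 2.2%. The same test under simple randomisation has 2.7%, and the stratified exact test 2.9%. Omitting the stratum thus costs about 0.5 to 0.7 of the 2.8 points missing from 5%. Discreteness accounts for most of the rest.

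**GEE, N=60, five visits, blocks of 4** (independence working correlation, z-test):

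| Model and SE | Size | Power, halved | Power, 40% cleared |
|---|---|---|---|
| No strata, plain sandwich | 3.3% | 93.8% | 59.5% |
| Strata, plain sandwich | 5.9% | 95.8% | 66.4% |

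The gains are 2.0 and 6.9 points, but the second row exceeds 5%, so part of the gain is bought with size. With strata and a Mancl-DeRouen standard error, size is 3.6% (five visits) and 4.5% (six visits). A check of 6,000 runs with that correction in both models gave power rising from 92.7% to 94.4% (halved) and from 55.4% to 60.0% (40% cleared) when strata were added.

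Nothing was computed for censored regression. It is included by the same reasoning only.

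**The case against.** Section 13.4.1 is silent, and a reader might infer that the plan has decided to ignore the strata. The text does not support that: a stratified conditional test is still an exact test of proportions, and a GEE model can carry covariates. What stands is that an analyst could follow the section to the letter and run the plain versions.

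A reader might also infer that leaving out the strata pushes the error rate of all these tests far below 5%. That does not hold. GEE is only mildly conservative: about 3% on the 13.3 counts, and 3.1 to 6.0% under Table 11's own models. The exact test is well below 5%, but mainly because it is discrete with few events. With 30 per arm and the same average SNR but no stratum effect, its size would still be only 1.7 to 1.8%. The 1.4% also depends on exactly equal arms: moving one man (31/29 or 29/31) raises it to 2.7%.

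The prognostic contrast is modelled, not observed. It rests on 34 men with any positive sample, a beta form and no decline over time, although 13.3 warns that detection may fall and that the kind of heterogeneity is unclear. Under Table 11's constant p=.5 the stratum carries no information and stratifying gains almost nothing.

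Mid-p is a separate choice with its own gain. With 18/18 and 12/12 splits, unstratified mid-p alone gives 30% and 81% power, against 22% and 75% plain and 25% and 77% stratified exact.

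Finally, these are secondary analyses with no stated alpha, and the errors are on the conservative side. All of this limits the size of the point. It does not remove the mismatch between 13.4 and 13.4.1.

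**Conclusion.** The point holds as a modest, free improvement to the secondary efficacy analyses. Run unstratified, the SNR exact test has a true size of about 1.4 to 2.2%, partly from discreteness (the larger part) and partly from the omitted stratum. GEE has about 3%. Stratifying recovers about 2 to 10 power points for SNR, depending on the allocation. For GEE it recovers about 2 points (detection halved) and 6 to 7 points (40% cleared) with the plain sandwich error, and somewhat less once the error is corrected for small samples. Stratifying the exact test does not by itself restore 5%.

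The figures assume the beta fit to the 13.3 counts, 60 men, exchangeable visits, no country effect, complete data, two-sided 5% tests, and either an even split or blocks of 4. A weaker stratum shrinks the gain and a stronger one enlarges it. The primary ANR test is already stratified, so its conclusion does not change.

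**What to change.** Amend 13.4.1 to say that:
- SNR is compared with an exact conditional test stratified by country and number of detectable screening samples. The mid-p value may be reported as well, with the note that it does not guarantee size at or below 5%; the ordinary stratified exact p-value does.
- The GEE and censored-regression models include both stratification factors.
- For GEE, significance comes from a named small-sample-corrected standard error or from the stratified permutation distribution already planned for the primary test. Adding strata with the plain sandwich error is not enough, because it runs at about 6%.

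The cost is a few sentences, with no extra data, visits or participants. Naming the covariates and the variance estimator in advance also closes the choice between GEE versions.
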